1 INTRODUCTION

This SAP contains technical and detailed elaboration of the principal features of the analysis described in the protocol and includes procedures for executing the statistical analysis to fulfil the objectives of the study.

The study was designed to be, and executed as, a double-blinded with an OLE. The OLE was removed from protocol version 9.0 and so, the use of the present tense is no longer accurate. In addition to the objectives and endpoints defined in Study 0367-CL-1201 protocol (core protocol), some additional objectives and endpoints specific to the Mayo Clinic (Minnesota) had been defined in Study 0367-CL-1201 [MAYO] Protocol. However, as there have been no participants recruited to the protocol from the Mayo sites, therefore there will be no SAP created. Until protocol version 7.0, the double-blinded period was 52 weeks and open label extension period was 24 weeks. However, from protocol version 8.0 onwards, the doubleblinded period was revised to 24 weeks and in protocol version 9.0 the OLE period was removed. Since no participants have been evaluated under protocol version 8.0 or later, two SAPs will be prepared: one for analyses up to 52 weeks of treatment (the double-blind part of the study), and the other one for analyses at the end of 76 weeks of treatment (the doubleblind part and the OLE part of the study). In analysis for the double-blind part and the OLE part of the study, participants assigned ASP0367 in the double-blinded period will be analyzed for through the double-blinded part and the OLE part of the study including followup visit, while participants switched from Placebo to ASP0367 in the OLE part will be analyzed in the OLE part only including follow-up visit.

This document is an analysis plan for 52 weeks (double-blinded part) including follow-up visit which correspond to protocol v7.0. However, inferential analyses for efficacy endpoints will be conducted at week 24 aligned with protocol v9.0.

Analyses for pharmacokinetic and pharmacodynamic (target gene expression and biochemical markers) endpoints, including exposure-response assessment, will be described in the separate analysis plan and this SAP only focus on efficacy and safety endpoints.

This document will be finalized prior to the database lock at the end of study. If there are any changes from the planned analyses in the final version of the SAP that impact the statistical analyses, then it will be documented in the CSR.

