•	To assess the relationship between functional improvement and biochemical markers, as well as gene expression-based pharmacodynamic biomarkers	•	Change from baseline in the levels of serum and urinary biomarkers (serum FLNC, CYC, ALDOA and urinary TITIN) at weeks 12 and 24 Relative change from baseline of whole blood PPARδ target gene expression levels at weeks 12 and 24 [†]

Note: Placebo comparison will be up to 24 weeks and will not include open-label extension.

5XSTS: 5 times sit to stand; 6MWT: 6-minute walk test; ALDOA: aldolase A; C_{ave, ss}: average plasma concentration at steady state; C-SSRS: Columbia-Suicide Severity Rating Scale; C_{trough}: concentration immediately prior to dosing at multiple dosing; CYC: cytochrome c; ECG: electrocardiogram; EQ-5D-5L:

European Quality of Life 5-dimension, 5-level questionnaire; EQ-VAS: EuroQol visual analogue scale; FLNC: filamin-C; MFIS: modified fatigue impact scale; Neuro-QoL: Quality of Life in Neurological Disorders; PGIC: patient global impression of change; PGIS: patient global impression of severity; PPARδ: peroxisome proliferator-activated receptor delta; TEAE: treatment emergent adverse event.

†Blood samples will be collected and stored appropriately over the course of the study and then analyzed.

Estimands

Primary estimand will be defined by the following 5 attributes:

- Treatment: ASP0367 or placebo
- Population: Participants with PMM, as defined by the inclusion/exclusion criteria of the study.
- Endpoint: Change from baseline in distance walked on the 6MWT at week 24.
- Intercurrent events and their corresponding strategies (see table below).
- Population level summary: Difference in change from baseline in distance walked on the 6MWT at week 24 between ASP0367 group and placebo group.

Intercurrent Events	Strategies to Handle Intercurrent Events
Treatment Discontinuation Due to Any Reason	For those participants who discontinued treatment, all observations after treatment discontinuation (Date of Last Study Drug Taken + 7 days) will be ignored. Analysis will be conducted assuming those participants remained assigned treatment and the condition that was observed before treatment discontinuation will continue, i.e., hypothetical strategy.

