6 STATISTICAL METHODOLOGY

6.1 General Considerations

Continuous data will be summarized descriptively including the number of participants (n), mean, standard deviation (SD), median, minimum and maximum. Categorical data will be summarized by frequencies and percentages. Percentages by categories will be based on the

number of participants with no missing data, i.e. the percentages for the non-missing categories will add up to 100%.

There are 4 different groups defined based in the randomization group in double-blind treatment period of the study:

- ASP0367 30 mg: Participants randomly assigned to 30 mg of ASP0367 during double-blind treatment period.
- ASP0367 75 mg: Participants randomly assigned to 75 mg of ASP0367 during double-blind treatment period.
- ASP0367 any dose: Participants randomly assigned to 30mg or 75 mg of ASP0367 during double-blind treatment period.
- Placebo group: Participants randomly assigned to placebo during double-blind treatment period.

Summaries based on FAS (e.g. efficacy data) will be presented by analysis group (ASP0367 30 mg group, ASP0367 75 mg group or placebo group), unless specifically stated otherwise. Statistical model and inference based on FAS will be performed and obtained by analysis group. To control the family-wise type I error under the nominal significance level of 10% 2-sided, the hierarchical testing procedure in the following order (Comparison between ASP0367 75 mg and placebo; Comparison between ASP0367 30 mg and placebo) will be applied in the primary analysis.

Safety analysis and other summaries based on SAF will be presented by analysis group (ASP0367 30 mg group, ASP0367 75 mg group or placebo group), unless specifically stated otherwise.

All data summarization and analyses will be performed using SAS® Version 9.4 or higher on Linux. Specifications for table, figures, and data listing formats can be found in the TLF specifications.

For continuous variables that are recorded as "<X", "<=X", ">X", or ">=X", the value of "X" will be used in the calculation of summary statistics if otherwise noted. This approach may result in a summary that reflects the presence of an analyte (such as troponin) when in fact the analyte was not detected but report as less than the lower limit of detection by the assay.

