6.8 Additional Conventions

6.8.1 Analysis Windows

Day 1 and Day -1 are defined as the day of start taking the IP and its prior day, respectively.

The following analysis window will be used.

The data summary by visits will be done following the analysis windows specified in the table below:

Analysis Visits	Scheduled Day in	Analysis Windows (day)
	Protocol	
Screening	Day -28	-35 to -14
Week 0 (Baseline)	Day -2 to 1	-2 to 1
Week 1	Day 8	5 to 13
Week 2	Day 14	14 to 18
Week 3	Day 22	19 to 25
Week 4	Day 29	26 to 42
Week 8	Day 57	43 to 70
Week 12	Day 85	71 to 98
Week 16	Day 113	99 to 126
Week 20	Day 141	127 to 154
Week 24	Day 169	155 to 182
Week 28	Day 197	183 to 210
Week 32	Day 225	211 to 238
Week 36	Day 253	239 to 266
Week 40	Day 281	267 to 294
Week 44	Day 309	295 to 322
Week 48	Day 337	323 to 350
Week 52	Day 365	351 to 378
End of Double Blind Part	Day 365	2 to 378
Follow-up	The last dose + 28	The last dose + 28 days to the last dose +
-	days	35 days

For the analyses of safety and efficacy, for all analysis visits excluding follow-up visit, the data "by the last dose + 7 days" and the data before the first dose date of open label extension part will be included.

If more than one observation exists within the analysis window, the observation closest to the scheduled visit day will be selected for that visit. If there are two observations that have the same distance from the scheduled day, the value that is after the scheduled day will be selected in the analysis. If more than one observation is made on the same day, an average value if continuous or the worst value if categorical will be included in the analysis.

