6.8 Additional Conventions

6.8.1 Analysis Windows

Day 1 and Day -1 are defined as the day of start taking the IP and its prior day, respectively. The following analysis window will be used. The data summary by visits will be done following the analysis windows specified in the table below:

Analysis Visits	Scheduled Day in	Analysis Windows (day)
	Protocol	, , ,
Screening	Day -28	-35 to -14
Week 0	Day -2 to 1	-2 to 1
Week 1	Day 8	5 to 13
Week 2	Day 14	14 to 18
Week 3	Day 22	19 to 25
Week 4	Day 29	26 to 42
Week 8	Day 57	43 to 70
Week 12	Day 85	71 to 98
Week 16	Day 113	99 to 126
Week 20	Day 141	127 to 154
Week 24	Day 169	155 to 182
Week 28	Day 197	183 to 210
Week 32	Day 225	211 to 238
Week 36	Day 253	239 to 266
Week 40	Day 281	267 to 294
Week 44	Day 309	295 to 322
Week 48	Day 337	323 to 350
Week 52	Day 365	351 to 378
Week 56	Day 393	379 to 406
Week 60	Day 421	407 to 434
Week 64	Day 449	435 to 462
Week 68	Day 477	463 to 490
Week 72	Day 505	491 to 518
Week 76	Day 533	519 to 560
End of Treatment	Day 533	2 to 560
Follow-up	The last dose + 28	The last dose + 28 days to the last dose +
_	days	35 days

For all analysis visits excluding follow-up visit, the data "by the last dose + 7 days" will be included.

For participants who received ASP0367 on the double blind part, all analysis visits will be used. For participants received placebo on the double blind part, baseline and analysis visit at and after the first ASP0367 taken will be used.

If more than one observation exists within the analysis window, the observation closest to the scheduled visit day will be selected for that visit. If there are two observations that have the same distance from the scheduled day, the value that is after the scheduled day will be selected in the analysis. If more than one observation is made on the same day, an average value if continuous or the worst value if categorical will be included in the analysis.

For Placebo to ASP0367 group, the measurement at week 52 is used as baseline, and for ASP0367 groups, the measurement at week 0 is used as baseline, unless otherwise specified.

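### 52-week SAP 6.8.1 frees the Follow-up row from the open-label cut-off, so, applied as written, the placebo Follow-up row could hold data collected after the switch to ASP0367

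*SAP*

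**What the plan says.** The 52-week SAP states its scope in section 1: "This document is an analysis plan for 52 weeks (double-blinded part) including follow-up visit which correspond to protocol v7.0". By-visit summaries follow the windows in 6.8.1. The governing sentence there begins "For the analyses of safety and efficacy, for all analysis visits excluding follow-up visit, the data", sets the limit of last dose + 7 days, and ends "and the data before the first dose date of open label extension part will be included". The Follow-up window is "The last dose + 28 days to the last dose" + 35 days. Section 6.8.1 does not say whether this is the last double-blind dose or the last dose of any study drug, although section 6.3 defines a last-dose date for the double-blind part.

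The placebo analysis group in 6.1 is "Participants randomly assigned to placebo during double-blind treatment period". A participant who later took open-label ASP0367 therefore stays in that column.

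Two statements in the same SAP point the other way. Describing the combined double-blind and OLE analysis, section 1 says "while participants switched from Placebo to ASP0367 in the OLE part will be analyzed in the OLE part only including follow-up visit". The note to the objectives table in 2.1 says "Placebo comparison will be up to 24 weeks and will not include open-label extension".

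**The concern.** The exemption has a sound purpose, because a visit 28 days after the last dose can never meet a 7-day limit. But the OLE limit sits in the same sentence and is lifted with it. No other rule in 6.8.1 keeps open-label data out of the Follow-up row.

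Safety relative to placebo is a primary objective. The 52-week SAP is the place where a placebo column exists: the 76-week SAP has only an any-dose ASP0367 group and a placebo-to-ASP0367 group. If a programmer follows 6.8.1 literally, the placebo Follow-up row can include people who have already taken ASP0367. That row would then not be a clean placebo reference for laboratory values, vital signs, ECG or weight.

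**Working it through.** The plan gives no figure to reproduce. The check is day arithmetic plus a search for other cut-offs.

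**Inputs.** Follow-up window: last dose + 28 to + 35 days (52-week SAP 6.8.1). Week 52: scheduled day 365, window 351-378 (same table). OLE visits from the 76-week SAP 6.8.1: "Week 56 Day 393 379 to 406", and Week 76 on day 533. The OLE lasted 24 weeks (section 1), and 533 - 365 = 168 = 24 × 7, so the schedule leaves no gap before it.

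**Reading A: last dose means last double-blind dose.**
- Day 365: 365 + 28 = 393 and 365 + 35 = 400. The window 393-400 lies inside the Week 56 window 379-406 and starts on the scheduled Week 56 day.
- Earliest Week 52 day: 351 + 28 = 379 and 351 + 35 = 386.
- Latest Week 52 day: 378 + 28 = 406 and 378 + 35 = 413.
- For a participant who rolls over without a gap of at least 28 days, all these windows fall after the first OLE dose. When several records qualify, 6.8.1 takes the one closest to the scheduled day, here day 393.

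**Reading B: last dose means last dose overall.**
- 533 + 28 = 561 and 533 + 35 = 568. This is the visit after the OLE; protocol 4.2.1 places follow-up after the OLE in the original design. A placebo rollover has by then had up to 24 weeks of ASP0367.

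On either reading, a placebo rollover has only post-switch data in the window.

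**Which outputs have another cut-off (52-week SAP)?**

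| Output | Section | Own OLE cut-off? |
|---|---|---|
| TEAEs | 5.4.1 | Yes |
| Deaths | 6.5.1 | Yes |
| AESIs (troponin, cardiac, CK) | 6.5.1 | Yes, because each requires a TEAE |
| Amylase, lipase, troponin thresholds | 6.5.2 | Yes |
| Liver thresholds | 6.5.2.1 | Yes |
| C-SSRS | 6.5.5.2 | Yes, for all analysis visits with no Follow-up exemption |
| By-visit laboratory values | 6.5.2 | No |
| Vital signs | 6.5.3 | No |
| ECG and QTcF | 6.5.4 | No |
| Body weight | 6.5.5.1 | No |

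**Comparison with the 76-week SAP.** Its parallel sentence in 6.8.1 exempts Follow-up from the 7-day limit alone, which is all that a Follow-up visit needs.

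**Number affected.** Not given. Assuming 1:1:1 allocation of the 33 interim participants, 33 / 3 = 11 were on placebo, so the range among those 33 is 0 to about 11.

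**The case against.** The best defence is that nothing in the SAP instructs anyone to tabulate open-label data as placebo. Sections 1 and 2.1 show the opposite intent, and the exemption was evidently written for the 7-day limit. That stands as a statement of intent, and it makes this a drafting slip rather than a chosen analysis. It does not remove the problem: 6.8.1 is the operative rule for the by-visit tables, and its wording conflicts with those sections and with 6.5.5.2.

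A reader might infer that placebo safety data in general are contaminated, or that a drug effect would be hidden. The documents do not support that. The outputs with their own cut-offs are protected, Weeks 1 to 52 are covered by the limits in 6.8.1, and no test is planned on the Follow-up row.

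A reader might also infer that the Follow-up row for the ASP0367 arms would hold on-drug values. That can arise only on reading A. On reading B, those participants are 28 to 35 days off drug. With the longest mean half-life in protocol 2.2.3.2, 17.5 hours, 28 × 24 / 17.5 = 38.4 half-lives have passed. Placebo rollovers are then also off drug, though previously exposed.

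Finally, the version 7.0 OLE schedule is not in the documents. On reading A it is not known what was measured at Week 56. The 76-week SAP lists efficacy assessments at weeks 64 and 76 but not 56. In version 9.0 the intermediate phone visits collect mainly abbreviated biochemistry. This limits reading A to whatever was recorded then.

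**Conclusion.** The point holds as a conflict within the 52-week SAP with a narrow effect. As written, 6.8.1 lets placebo participants who entered the OLE contribute to the placebo Follow-up row of four sets of by-visit tables, and only with post-switch data.

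Reading A assumes that the participant entered the OLE without a gap of 28 days or more and that the measurement was made around Week 56. Reading B needs only that the follow-up visit took place in its window. The effect on the row cannot be sized, because the number of rollovers is not stated. The primary 6MWT analysis at week 24 is untouched. The correction is worth making because it is cheap and the row otherwise contradicts the SAP's own scope, but it does not call the main safety outputs into question.

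**What to change.** In 6.8.1 of the 52-week SAP:

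- Exempt Follow-up from the limit of last dose + 7 days only.
- Define last dose in the Follow-up row as the date of last study drug taken in the double-blind part, as already defined in section 6.3.
- Exclude data on or after the first OLE dose from the Follow-up row.

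Post-OLE follow-up stays in the 76-week SAP. If the 52-week SAP is already final, document the change in the clinical study report, as section 1 provides.

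The cost is one sentence and one programming condition. The downside is a smaller n in the Follow-up row, which would then consist essentially of participants who did not continue into the OLE.

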Exercise status ^q	Х	Х	Х	Х	Х	Х	Х	Х	Х	Х	Х	Х
Adverse event assessment	Х	Х	Х	Х	Х	Х	Х	Х	Х	Х	Х	Х

5XSTS: 5 time sit to stand; 6MWT: 6-minute walk test; ALDOA: aldolase A; CK: creatine kinase; C-SSRS: Columbia-Suicide Severity Rating Scale; CYC: cytochrome c; ECG: electrocardiogram; EOS: end of study; EOT_P2: end of treatment during double-blind treatment period; EQ-5D-5L: European Quality of Life 5-dimension, 5-level

24 Jan 2024 *Footnotes* Version 9.0 Substantial Amendment 8

- CONFIDENTIAL -

questionnaire; FLNC: filamin-C; IP: investigational product; MB: isoenzymes found in heart muscle; MFIS: Modified Fatigue Impact Scale; MM: isoenzymes found in skeletal and heart muscle; Neuro-QoL: Quality of Life in Neurological Disorders; PGIC: Patient Global Impression of Change; PGIS: Patient Global Impression of Severity; PPARδ: peroxisome proliferator-activated receptor delta; QTcF: QT interval using Fridericia's correction; WOCBP: women of childbearing potential

- a. All assessments at the study site visit may be performed over 2 to 3 days. Assessments scheduled for each study site visit should be completed within visit window.
- b. The site will perform follow-up phone call visits. Blood sample collection and ECG will be performed by qualified healthcare provider from the home healthcare vendor (ECG will be performed at weeks 2 and 8 only). In case the home healthcare visit is not feasible, the visit can be conducted at the study site.
- c. IP administration should be started after the completion of assessments at week 0, except for postdose blood sampling for pharmacokinetics. The day participants start taking the IP is considered as day 1.
- d. Participants who discontinue the study treatment will visit the site and perform EOT_P2 assessments. Participants will be encouraged to visit the study site for EOT_P2 assessments as soon as the discontinuation of the study treatment. Participants who discontinue the study will be followed until the EOS visit. Participants who remain in the study for efficacy and safety evaluations will continue to follow the schedule of assessments without IP dosing.
- e. To be performed prior to randomization.
- f. Vital signs will be taken prior to blood draw. Blood pressure and pulse will be measured in the sitting or supine position after the participant has rested for at least 5 minutes.

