6 INVESTIGATIONAL PRODUCT(S)

6.1 Investigational Product(s) Administered

Table 4Investigational Product(s)

Name	ASP0367	Placebo for ASP0367	
Use	Test product	Placebo	
Dosage Form	Tablets	Tablets	
Physical Description	Round, light yellowish red film-coated tablet	Matching placebo for ASP0367	
Unit Dose Strength	10 and 25 mg	Matching placebo for ASP0367	
Inactive Excipients	Lactose monohydrate, croscarmellose sodium, hydroxypropyl cellulose, microcrystalline cellulose, magnesium stearate, hypromellose, polyethylene glycol, talc, titanium dioxide, yellow ferric oxide, red ferric oxide	Mannitol, microcrystalline cellulose, croscarmellose sodium, magnesium stearate, hypromellose, polyethylene glycol, talc, titanium dioxide, yellow ferric oxide, red ferric oxide	
Storage	20°C to 25°C (68°F to 77°F); excursions permitted between 15°C and 30°C (59°F and 86°F) (as per USP Controlled Room Temperature). Protect from light.	20°C to 25°C (68°F to 77°F); excursions permitted between 15°C and 30°C (59°F and 86°F) (as per USP Controlled Room Temperature). Protect from light.	
Packaging and Labeling	HDPE bottles	HDPE bottles	
Route of Administration	Oral	Oral	
Administration	Once daily with or without food Participants should be instructed to take the IP in the morning at the same time each day as much as possible. Crushing of tablets is not allowed.	Once daily with or without food Participants should be instructed to take the IP in the morning at the same time each day as much as possible. Crushing of tablets is not allowed.	
IMP or Non-IMP	IMP	IMP	
Sourcing	Provided centrally by sponsor	Provided centrally by sponsor	

HDPE: High-density polyethylene; IMP: Investigational Medicinal Product; IP: investigational product; USP: US Pharmacopeia

The anticipated duration of the study for each participant, including screening and follow-up, is approximately 32 weeks.

Participants should be instructed to take the IP in the morning at the same time each day as close as possible. Crushing of tablets is not allowed. IP will be administered orally with or without food.

At study site visits, participants will visit the study site without taking the IP and take IP at the study site as instructed.

Arm/IP Name	ASP0367	Placebo	
Use	Test product	Matching placebo for ASP0367	
Dose	75 mg (3 × 25 mg tablet) 30 mg (3 × 10 mg tablet)	NA (3 \times tablet)	
Frequency	Once daily	Once daily	
Route	Oral	Oral	
Duration	24 weeks	24 weeks	

Table 5Treatment Groups and Duration

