5 EFFICACY AND SAFETY ENDPOINTS

5.1 Primary Efficacy Endpoint (6-minute Walk Test)

The 6MWT will be performed indoors, along a long, flat, straight, enclosed corridor with a hard surface that is seldom traveled. The total distance walked by a participant, as well as distance per minute will be calculated by rounding to the nearest meter and recorded. The 6MWT will be video recorded for quality purposes.

Participants will be asked to wear comfortable clothing and appropriate shoes for walking. A light meal is acceptable before early morning or early afternoon tests. Participants will be recommended not to have exercised within 2 hours prior to beginning of the test. A "warm up" period before the test will not be performed. Participants will sit at rest in a chair located near the starting position for at least 10 minutes before the test starts. The test will be performed at weeks 0, 4, 12, 24, 36 and 52.

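### The 52-week SAP cuts by-visit data strictly before the date of the first open-label dose, so pre-dose week-52 records dated that day can drop out of the descriptive double-blind summaries

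*SAP*

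**What the plan says.** The SAP file holds two plans, one for the 52-week double-blind part and one for up to 76 weeks including the OLE.

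- **52-week SAP, 6.8.1.** "For the analyses of safety and efficacy, for all analysis visits excluding follow-up visit", data are accepted up to the last dose plus 7 days, and "the data before the first dose date of open label extension part will be included". The two limits are joined by a plain *and*. Section 6.5.5.2 repeats the rule for C-SSRS.
- **52-week SAP, 5.1.** On the 6MWT: "The test will be performed at weeks 0, 4, 12, 24, 36 and 52". The other efficacy scores have the same visits, except that PGIC has no week 0. The Week 52 window is days 351 to 378 around day 365. The End of Double Blind Part row takes the record closest to day 365 from days 2 to 378.
- **76-week SAP, 6.8.1.** "For Placebo to ASP0367 group, the measurement at week 52 is used as baseline". The footnote to the baseline table (6.2.3) and the body weight section (6.5.5.1) say the same.
- **Protocol 6.1.** At site visits, "participants will visit the study site without taking the IP and take IP at the study site as instructed".
- **Protocol Table 1, footnote a.** "All assessments at the study site visit may be performed over 2 to 3 days".

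**The concern.** The cut compares dates, not times relative to dosing. If a participant completes the week-52 assessments and takes the first open-label dose on the same day, those assessments precede any open-label exposure, yet they fail a rule that asks for an earlier date. Nothing in either SAP rescues them.

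At stake are the descriptive Week 52 and End of Double Blind Part values for laboratory tests, vital signs, ECG, weight, C-SSRS and efficacy scores. The loss would be selective, because it can only strike participants who entered the OLE. The Week 52 row would then lean towards those who did not continue or whose assessments happened to be dated earlier.

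The two plans also disagree. For a placebo rollover, the same value is an acceptable baseline before ASP0367 in one and excluded from the double-blind data in the other.

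**Working it through.** The plan states no figure to reproduce, so the check applies the rule to example records. Let A be the assessment day, O the day of the first OLE dose and L the day of the last double-blind dose. The section does not say which last dose it means. I take the last double-blind dose, as the same SAP's TEAE definition (5.4.1) does.

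Limit 1: A ≤ L + 7. Limit 2: A < O.

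| A | O | L | Limit 1 | Limit 2 | Both required | Either suffices |
|---|---|---|---|---|---|---|
| 365, pre-dose | 365 | 364 | 365 ≤ 371, met | 365 < 365, not met | dropped | kept |
| 364 | 365 | 364 | 364 ≤ 371, met | 364 < 365, met | kept | kept |
| 363 | 365 | 364 | 363 ≤ 371, met | 363 < 365, met | kept | kept |
| 365 | 366 | 365 | 365 ≤ 372, met | 365 < 366, met | kept | kept |
| 368, on open label | 365 | 364 | 368 ≤ 371, met | 368 < 365, not met | dropped | kept |

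The first row is the problem under the *both* reading: a valid double-blind record is lost. The last row is the problem under the *either* reading: a record three days into open-label treatment enters a double-blind row.

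**Which reading is meant.** Protocol 9.4.2.1 (6MWT data) and the 52-week SAP's TEAE and threshold rules (5.4.1, 6.5.2, 6.5.2.1) all end at the earliest of several limits. That supports requiring both.

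**Fallback.** With the day-365 record dropped, the scheduled post-baseline efficacy days left are 29, 85, 169 and 253. The closest to 365 is day 253 (week 36): 365 − 253 = 112 days = 16 weeks. It lies outside 351 to 378, so the Week 52 row is empty for that participant. For a safety measure taken at week 48 (an assumption, since the version 7.0 schedule is not given), the fallback is day 337: 365 − 337 = 28 days.

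**How the plans treat similar records.** The 52-week SAP's Week 0 window runs from day −2 to day 1, so it keeps assessments made on the first dosing day. Protocol 9.4.1 defines baseline relative to first administration, as does the 76-week SAP (6.5.2) for CK-MM and CK-MB. Only the OLE transition uses a strict date.

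**What is outside the rule.** TEAEs and the amylase, lipase, troponin and liver threshold tables have their own period, ending at the move to the OLE. The week-24 window ends on day 182, well before day 351.

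**The case against.** The strongest reply is that same-day dosing is not shown. All participants took part under protocol version 7.0 or earlier, and that OLE schedule is not in the documents. Protocol 6.1 and the assessment order in Table 6 belong to version 9.0, which has no OLE and no week-52 visit. Assessments may also spread over 2 to 3 days. This stands, and it limits the claim to records that share the OLE dose date. Same-day dosing remains the likely pattern, given dosing at site visits and week 52 as the baseline before ASP0367, but that is inference.

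A reader might go further and infer that every OLE entrant loses all week-52 data. The documents do not support this. The day numbers do not help: 393 − 365 = 28 is only the four-weekly visit grid, and it would be the same if the first OLE dose fell on day 366 or 370. Nor are all placebo-controlled tables affected, as the TEAE and threshold rules show.

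It is also fair to say that week-52 safety values do not vanish. The 76-week SAP uses all visits for participants randomized to ASP0367, and week 52 as baseline for placebo rollovers. However, it pools the doses, has no concurrent placebo comparison and plans no efficacy analysis, so it does not replace the lost display.

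Finally, the SAP confines the placebo comparison to 24 weeks and inferential efficacy to week 24, and the study was stopped for futility. That stands too: no planned test depends on week 52. The defect is in descriptive tables.

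**Conclusion.** The wording needs repair under either reading. If both limits apply, a pre-dose week-52 record dated on the first OLE dose day is excluded from the descriptive Week 52 and End of Double Blind Part summaries, in conflict with the 76-week SAP's baseline rule. If either suffices, open-label data up to 7 days after the last double-blind dose can enter double-blind rows.

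Per affected participant, the End of Double Blind efficacy value moves back 16 weeks and the Week 52 value is missing. The number of such participants cannot be computed, since neither the count reaching week 52 nor any first OLE dose date is given. The conclusion assumes that the last dose means the last double-blind dose, and it bites only where assessment and first OLE dose share a date. Primary inference at week 24 is unaffected.

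**What to change.** In 6.8.1 and 6.5.5.2 of the 52-week SAP, state that both limits must be met, and replace the second limit with: *up to and including the date of the first OLE dose, if collected before that dose; scheduled week-52 visit assessments on that date with no recorded time are treated as pre-dose*. This matches the baseline rule of the 76-week SAP.

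The cost is one sentence in two sections and a small change to the date comparison in programming, recorded in the CSR as SAP section 1 provides. The downside is that an untimed same-day record could occasionally be post-dose.
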